5.2. Safety Variables

Safety variables include recording, measurements, or laboratory test results for individual subjects of the following: TEAEs, vital signs (including pulse rate, blood pressure, respiration rate, and body temperature), targeted physical examination findings, results of laboratory tests (including hematology, blood chemistry, pregnancy test), and diagnostic assay for SARS-CoV-2 infection (at baseline for all subjects; and at the time when signs of COVID-19 are identified in subjects).

5.3. Pharmacokinetic Variables

The PK variables are concentrations of casirivimab and imdevimab in serum and time. The sampling time points are specified in [Table 3](#).

5.4. Immunogenicity Variables

The immunogenicity variables are ADA status, titer, and NAb status at nominal sampling time/visit. Serum samples for ADA will be collected at the visits specified in [Table 3](#). Samples positive in the ADA assays will be further characterized for ADA titers and when feasible, NAb status.

5.5. Other Variables

Other variables include anti-SARS-CoV-2 serology test results and time, and COVID-19-related medically-attended visits. The sampling time points are specified in [Table 3](#).

6. STUDY DESIGN

6.1. Study Description and Duration

This is an open label, phase 2a study to assesses the PK, safety, tolerability, and immunogenicity of casirivimab+imdevimab in subjects <12 years old who are not infected with SARS-CoV-2 but are at high risk to develop severe COVID-19 if they become infected. Risk factors are defined as inclusion criteria in Section [7.2.1](#)). A diagram depicting the study design is provided in [Figure 1](#). The Schedule of Events is provided in Section [9](#).

Subjects will be assessed for eligibility during the screening period, which may occur up to 7 days prior to the day 1 (baseline) visit. To be eligible, subjects must not have symptoms consistent with

COVID-19, and must be confirmed negative for SARS-CoV-2 infection prior to study drug administration according to the window specified in the exclusion criteria.

This study will enroll subjects into two analysis groups at baseline, with each group defined according to body weight (Section 11.4.4.1). All subjects will receive a single dose of casirivimab+imdevimab, adjusted for body weight as described in Section 8.1. Each subject will be observed for one hour after completion of dosing, and the subject (or their parent or guardian) will be contacted by phone within 24 hours of dosing to assess for any potential adverse events (AEs).

Following dose administration, subjects will be followed for approximately 24 weeks (169 days) to monitor for TEAEs. At each scheduled site visit, the investigator or designee will assess and document the subject's general health and adverse events since the last contact. If a scheduled visit cannot be performed in person (for example, due to COVID-19 restrictions), or if no assessments or collections require the subject to be contacted in person, the visit may be conducted virtually (ie, by telemedicine or phone). Grade ≥ 3 injection site reactions and grade ≥ 3 hypersensitivity reactions that occur after study drug administration will be captured as AESIs, to allow for expedited reporting. Multisystem inflammatory syndrome in children (MIS-C) will also be captured as an AESI.

During the first five weeks after study drug administration, subjects will have samples collected for clinical laboratory tests (hematology, blood chemistry), drug concentration, and immunogenicity. On day 1, subjects in group A and group B will each be assigned using an Interactive Web Response System (IWRS) to one of two staggered PK-ADA sampling schedules (schedule 1 and schedule 2).

6.2. Monitoring for Potential COVID-19

Subjects and their caregivers will be provided with contact information for the clinical study site and will be given written and verbal instructions to call site personnel with any changes in their health status. They will be asked to promptly notify site personnel by phone of any symptoms or signs potentially related to COVID-19. Additionally, subjects and their caregivers will be contacted regularly during the study for symptoms or signs of COVID-19.

In the event of suspected COVID-19, subjects will continue in the study and undergo additional unscheduled visits, as described in Section 6.3.

6.3. Management of Subjects With Suspected COVID-19

Unscheduled Visit to Confirm SARS-CoV-2 Infection and COVID-19 Symptoms. Subjects who have signs or symptoms consistent with COVID-19 will have an unscheduled visit to collect a mid-turbinate nasal swab sample for SARS-CoV-2 RT-qPCR testing and viral genome sequencing, evaluate signs and symptoms of COVID-19 (by the Investigator or designee), collect blood for drug concentration and immunogenicity, and (depending on the subject's weight category) collect blood for serology and exploratory research (Table 3).

Medical Management of SARS-CoV-2-Positive Subjects. Subjects with laboratory confirmed SARS-CoV-2 infection and/or the parent or guardian should be informed as soon as possible. Local or CDC guidance should be followed to reduce the risk of transmission. Subjects with acute illness

should be medically managed according to local standard of care and per the discretion of the treating physician.

Continuation of the Schedule of Events for SARS-CoV-2-Positive Subjects. Subjects with confirmed SARS-CoV-2 infection will continue to follow the Schedule of Events as planned. If a scheduled visit cannot be performed in person (for example, due to COVID-19 restrictions), or if no assessments or collections require the subject to be contacted in person, the visit may be conducted virtually (ie, by telemedicine or phone).

Additional Weekly Unscheduled Visits for Viral Testing of SARS-CoV-2-Positive Subjects. Subjects with confirmed SARS-CoV-2 infection will have weekly unscheduled visits to collect a mid-turbinate nasal swab sample for SARS-CoV-2 testing. These visits will include all assessments indicated in the ‘SARS-CoV-2 Confirmation’ visit in the Schedule of Events ([Table 3](#)). Note that these weekly visits will be held in addition to the visits that are planned as part of the study. If a weekly visit occurs within the same window as a planned visit, all assessments indicated in the ‘SARS-CoV-2 Confirmation’ visit must be performed during the planned visit. Assessments or samples that are indicated for both visits in the Schedule of Events will only be collected once. The weekly unscheduled visits will continue until two consecutive negative SARS-CoV-2 test results are obtained from samples collected ≥ 24 hours apart.

Additional Assessment of Adverse Events in SARS-CoV-2-Positive Subjects. Subjects with confirmed SARS-CoV-2 infection will be assessed by the Investigator or designee for adverse events ([Section 10.1](#)) and details of COVID-19-related medically-attended visits ([Section 9.2.4.6](#)). This assessment will occur at minimum on a weekly basis during the unscheduled visits described above. Subjects may be assessed for adverse events on a more frequent basis, if deemed clinically appropriate by the Investigator or designee. If more frequent assessments are performed, these will be reported as additional unscheduled visits.

[figure not shown]
Requirements for SARS-CoV-2 Testing During Unscheduled Visits. Any SARS-CoV-2 test conducted during an unscheduled visit will be recorded as a concomitant procedure and associated with the adverse event “COVID-19”. The preferred method of SARS-CoV-2 testing is by central laboratory RT-qPCR using a mid-turbinate nasal swab sample. Central laboratory samples that have been confirmed positive for SARS-CoV-2 may be used for exploratory viral sequencing analysis ([Section 9.2.8.4](#)).

Note: If a subject is unable or unwilling to visit the study site for SARS-CoV-2 testing as part of an unscheduled visit, central laboratory testing of a mid-turbinate swab sample may not be feasible. If this occurs, a local diagnostic assay (eg, molecular assay such as RT-PCR for SARS-CoV-2), using an appropriate sample such as nasopharyngeal, nasal, oropharyngeal, or saliva, is allowable.

The local diagnostic assay for SARS-CoV-2 must be considered acceptable for clinical use by local standards. If the test has not been approved or has not received authorization, such as EUA issued by the US FDA or authorization by the equivalent local health authority, the Sponsor must be consulted. The use of RT-PCR is highly recommended.

In the event that the subject obtains SARS-CoV-2 testing at a facility not affiliated with the site, study site personnel will attempt to obtain and record all information from SARS-CoV-2 tests conducted in local laboratories that are associated with other medical facilities. This information

will include test results, name of the assay(s) utilized, and whether the laboratory or laboratories conducting the assay(s) are CLIA certified (or equivalent).

Figure 1: Study Flow Diagram

The EOS visit will be performed in person. In the case that the day 169 visit was conducted prior to Amendment #2, the subject should return to the clinical trial unit for 1 additional visit for the EOS visit as soon as possible after Amendment #2 is approved by local regulatory and ethics as required.

6.4. Study Stopping Rules

The Sponsor will monitor safety data on an ongoing basis to assess the risk/benefit profile of casirivimab+imdevimab. The Sponsor team may be comprised of the medical/study directors, a Global Patient Safety representative, representatives from Biostatistics and Data Management, as well as representatives from Clinical Operations and Regulatory Affairs. The data to be reviewed will include, but are not limited to the following:

- TEAEs that result in an early study drug discontinuation
- Grade ≥ 3 TEAEs
- Treatment-emergent SAEs
- Treatment-emergent AESIs
- Selected laboratory tests, as deemed appropriate

If there are significant safety concerns, a recommendation may be made to temporarily pause, alter, or terminate the study. Appropriate action, if needed, will be taken based upon this review and in consultation with additional Sponsor team members, as needed. Applicable regulatory procedures will be adhered to as required by local laws in relation to any decisions related to a change in study conduct, temporary halt, study termination, or study restart.

6.5. End of Study Definition

The end of study is defined as the date the last subject completes the last study visit, withdraws from the study, or is lost to follow-up (ie, the subject can no longer be contacted by the Investigator).

6.6. Study Committees

6.6.1. Independent Data Monitoring Committee

An IDMC (Independent Data Monitoring Committee) will actively review data throughout the study to monitor patient safety and efficacy data. The IDMC can make recommendations about early study closure or changes to the study conduct. The operation of the IDMC is governed by a charter describing further details, such as procedures (including but not limited to periodic safety monitoring) and requirements for reporting its observations to the Sponsor. The IDMC will conduct periodic data reviews as detailed in the IDMC charter. These data reviews will include all available safety data, including deaths, from all enrolled study participants up to the cutoff date for the analysis.

6.6.2. Safety Monitoring Team

A safety monitoring team at Regeneron may meet periodically to review blinded safety data as needed. The team may be comprised of the medical directors, a Global Patient Safety representative, a Clinical Pharmacology representative and representatives from Biostatistics and Data Management, as well as representatives from Clinical Operations and Regulatory Affairs. The data to be reviewed include, but are not limited to:

- Treatment-emergent adverse events that result in an early study withdrawal
- Serious adverse events (SAEs)
- Selected laboratory tests, as deemed appropriate by the safety monitoring team
- Grade ≥ 3 injection-site reactions or grade ≥ 3 hypersensitivity reactions
- Multisystem inflammatory syndrome in children (MIS-C)
- Drug concentration

Appropriate action, if needed, will be taken based upon this review and in consultation with the medical monitor.

6.7. Planned Interim Analysis

No formal interim analysis is planned for the study. Interim reviews of PK and safety data may be performed before subjects complete the end of study.

7. SELECTION, WITHDRAWAL, AND REPLACEMENT OF SUBJECTS

7.1. Number of Subjects Planned

The study will enroll approximately 28 subjects <12 years. This includes at least 12 subjects with body weight ≥ 10 kg and <40 kg, and at least 12 subjects with body weight ≥ 3 kg to <10 kg. Sample size and dosing may be adjusted based on PK analyses conducted (Section 3.2.3).

Refer to Section 11.2 for justification of sample size.

7.2. Study Population

7.2.1. Inclusion Criteria

Subjects must meet the following criteria to be eligible for inclusion in the study:

1. Is <12 years of age and ≥ 3 kg to <40 kg at the time parental/guardian consent is signed
2. Has at least one risk factor for developing severe COVID-19 if they were to become infected, such as:
 - a. Obesity (BMI [kg/m^2]) $\geq 95^{\text{th}}$ percentile for age and sex based on CDC growth charts)
 - b. Cardiovascular disease
 - c. Chronic lung disease
 - d. Type 1 or type 2 diabetes mellitus
 - e. Chronic kidney disease, including those on dialysis
 - f. Chronic liver disease
 - g. Immunocompromised or immunodeficient, based on Investigator's assessment (examples include cancer treatment, bone marrow or organ transplantation, immune deficiencies, HIV infection, sickle cell anemia, thalassemia, and prolonged use of immune-weakening medications)

- h. Medical complexities (examples include any underlying genetic condition, neurologic condition, metabolic condition, or congenital heart disease)
- i. **Any other condition** deemed by the Investigator to be a risk factor for severe COVID-19

- 3. Is willing and able to comply with clinic visits and study-related procedures
- 4. Has provided informed consent signed by subject or legally acceptable representative

Note: Age-appropriate assent will be collected from the study subject according to local regulatory (competent authority/ethics) guidelines.

7.2.2. Exclusion Criteria

Subjects who meets any of the following criteria will be excluded from the study:

- 1. Has positive diagnostic test for SARS-CoV-2 infection from a sample collected during screening \leq 7 days prior to study drug administration
Note: The sample for the test should be collected \leq 7 days within study drug administration, and the result should be reviewed and confirmed negative prior to dosing. Historical records will not be accepted.
- 2. Has active respiratory or non-respiratory symptoms consistent with COVID-19 in the opinion of the Investigator
- 3. Has subject-reported clinical history of COVID-19, as determined by Investigator, within the last 90 days
- 4. Has subject-reported history of prior EUA/approved positive diagnostic test for SARS-CoV-2 infection within the last 90 days
- 5. Is currently hospitalized or was hospitalized for >24 hours for any reason within 14 days of the screening visit
- 6. Prior use (within 90 days prior to study drug administration) or current use of any investigational, authorized, or approved passive antibody for prophylaxis of SARS-CoV-2 infection, including convalescent plasma, convalescent sera, hyperimmune globulin, or other monoclonal antibodies (eg, bamlanivimab and etesevimab, sotrovimab)
- 7. Has initiated vaccination for SARS-CoV-2 with an investigational or approved vaccine, but has not completed the vaccine schedule as recommended by the vaccine manufacturer.
- 8. Plans to receive an investigational or approved SARS-CoV-2 vaccine within 90 days after study drug administration, or per the recommended time frame from the current Centers for Disease Control vaccination guidelines ([CDC, 2021b](#))
- 9. Has participated, is participating, or plans to participate in a clinical research study evaluating any authorized, approved, or investigational vaccine for COVID-19
- 10. Has a history of significant multiple and/or severe allergies (eg, latex gloves), or has had an anaphylactic reaction to prescription or non-prescription drugs or food

Note: This is to avoid possible confounding of the safety analysis and not due to any presumed increased risk of these individuals to a reaction to the investigational product.

11. Has a known allergy or hypersensitivity to components of the study drug
12. Has any physical examination findings, history of any illness, or any concomitant medications, that in the opinion of the investigator might confound the results of the study or pose an additional risk to the subject by their participation in the study
13. Has received any live vaccine within 4 weeks prior to study drug administration
14. Treatment with another investigational (not authorized or approved) agent in the last 30 days or within 5 half-lives of the investigational drug, whichever is longer, prior to the screening visit

7.3. Premature Withdrawal from the Study

A subject has the right to withdraw from the study at any time, for any reason, and without repercussion.

The Investigator and/or Sponsor have the right to withdraw a subject from the study if it is no longer in the interest of the subject to continue in the study, or if the subject's continuation in the study places the scientific outcome of the study at risk (eg, if a subject does not or cannot follow study procedures). An excessive rate of withdrawals would render the study uninterpretable; therefore, unnecessary withdrawal of subjects should be avoided.

Subjects who are withdrawn prematurely from the study will be asked to complete the early termination visit, as described in Section [9.1.2](#).

Rules for discontinuation of study treatment (permanent or temporary) are discussed in Section [8.2.2](#).

7.4. Replacement of Subjects

Subjects prematurely discontinued from study will not be replaced.

8. STUDY TREATMENTS

8.1. Investigational Treatments

The following drug product will be provided. Instructions on dose preparation are provided in the pharmacy manual.

Casirivimab+imdevimab, to be co-administered:

- Casirivimab: supplied as a 120 mg/mL solution for SC injection
- Imdevimab: supplied as a 120 mg/mL solution for SC injection

Subjects will receive a single dose of casirivimab+imdevimab, administered as 1 to 4 subcutaneous (SC) injections based on body weight. [Table 2](#) provides (according to body weight) the total dose, volume, route of administration, and number of injections that will be administered. This table also describes additional requirements and allowances for dose administration.

For study drug administration which requires multiple SC injections, it is recommended to use different quadrants of the abdomen (avoiding navel and waist areas) and/or upper thighs. Each

injection must be given in a different anatomical location (eg, 1 injection administered in the right lower quadrant of the abdomen, another in the left lower quadrant of the abdomen, etc). A numbing cream may be used at the planned site(s) of injection.

Table 2: Weight-Tiered Dosing of Casirivimab+Imdevimab

Weight-Tiered Dose Group	Total Dose (mg)	Route of Administration	Total Number of Injections	Total Volume (mL) of Injection ⁶
≥20 kg to <40 kg	792 (396 per mAb)	SC ³	4	6.6 (3.3 per mAb)
≥10 kg to <20 kg	408 (204 per mAb)	SC ³	2 or 4 ⁴	3.4 (1.7 per mAb)
≥5 kg to <10 kg ¹	144 (72 per mAb)	SC	1 or 2 ⁵	1.2 (0.6 per mAb)
≥3 kg to <5 kg ²	96 (48 per mAb)	SC	1	0.8 (0.4 per mAb)

¹ Subjects between 5 and 10 kg should not receive an injection containing more than 1.25 mL.

² Subjects <5 kg should not receive an injection containing more than 1 mL.

³ For SC injection, Investigators may use an infusion pump containing the combined volume with both mAbs. This may improve tolerability through administration of a single injection.

⁴ Study drug may be administered as 2 injections (1.7 mL of casirivimab and 1.7 mL of imdevimab) or 4 injections (0.8 mL of casirivimab, 0.9 mL of casirivimab, 0.8 mL of imdevimab, and 0.9 mL of imdevimab).

⁵ Study drug may be administered as 1 injection (1.2 mL total) or as 2 injections (0.6 mL of casirivimab and 0.6 mL of imdevimab).

⁶ The total volume of study drug per syringe and the number of injections will be recorded in the eCRF.

8.2. Dose Modification and Study Treatment Discontinuation Rules

8.2.1. Dose Modification

Dose modification for an individual subject is not allowed.

8.2.2. Study Drug Discontinuation

This is a single dose study; study drug discontinuation is not applicable.

8.3. Management of Acute Reactions

8.3.1. Acute Injection Reactions

8.3.1.1. Systemic Injection Reactions (Hypersensitivity)

Emergency equipment and medication for the treatment of systemic reactions must be available for immediate use. All systemic injection reactions must be reported as AEs (as defined in Section 10.2.1) and graded using the grading scales as instructed in Section 10.2.4.

Acute systemic reactions following SC injection of study drug should be treated using clinical judgment to determine the appropriate response according to typical clinical practice.

8.3.1.2. Local Injection Site Reactions

Local injection site reactions must be reported as AEs and graded according to Section 10.2.4.

8.4. Method of Treatment Assignment

This is an open-label study; subjects will receive the study drug on day 1 as assigned.

8.5. Blinding

This is an open-label study without blinding.

8.6. Treatment Logistics and Accountability

8.6.1. Packaging, Labeling, and Storage

Open-label study drug will display the product lot number on the label.

Study drug will be stored at the site at a temperature of 2°C to 8°C; storage instructions will be provided in the pharmacy manual.

8.6.2. Supply and Disposition of Treatments

Study drug will be shipped at a temperature of 2°C to 8°C to the Investigator or designee at regular intervals or as needed during the study. At specified time points during the study (eg, interim site monitoring visits), at the site close-out visit, and following drug reconciliation and documentation by the site monitor, all opened and unopened study drug will be destroyed at the site with approval by the Sponsor or returned to the Sponsor or designee.

8.6.3. Treatment Accountability

All drug accountability records must be kept current.

The Investigator must be able to account for all opened and unopened study drug. These records should contain the dates, quantity, and study medication

- Dispensed to each subject
- Disposed of at the site or returned to the Sponsor or designee.

All accountability records must be made available for inspection by the Sponsor and regulatory agency inspectors; photocopies must be provided to the Sponsor at the conclusion of the study.

8.6.4. Treatment Compliance

All drug compliance records must be kept current and made available for inspection by the Sponsor and regulatory agency inspectors.

8.7. Concomitant Medications and Procedures

Any treatment administered during the on-treatment period (Section 11.4.3.1) will be considered concomitant medication. This includes medications that were started before the study and are ongoing during the study.

All concomitant medications and procedures will be captured in the eCRF.

Any positive SARS-CoV-2 test conducted during an unscheduled visit will be recorded as a concomitant procedure and associated with the COVID-19 AE.

8.7.1. Prohibited Medications

The following are prohibited as concomitant medication (as defined in Section 8.7) when used as prophylaxis in SARS-CoV-2-negative individuals:

- Other investigational drugs
- Investigational SARS-CoV-2 vaccines
- Authorized or approved SARS-CoV-2 vaccines (only prohibited within 90 days after study drug administration, or per the recommended time frame from current Centers for Disease Control vaccination guidelines) ([CDC, 2021b](#))
- Investigational, authorized, or approved passive antibody for prophylaxis of SARS-CoV-2 infection, including convalescent plasma, convalescent sera, hyperimmune globulin, or other monoclonal antibodies (eg, bamlanivimab and etesevimab, sotrovimab) (only prohibited within 90 days after study drug administration)

Use of a prohibited medication during the on-treatment period may result in permanent discontinuation of a subject from the study.

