Length of Follow-up Period. Subjects will undergo a follow-up period of approximately 24 weeks (six months) for assessment of drug concentrations, safety, and immunogenicity. In COV-2069, a single 1200 mg SC dose resulted in an observed half-life of approximately 32.4 days (casirivimab) and 27.0 days (imdevimab). The duration of the follow-up period in the current study is thus intended to allow observation of drug concentration and safety in subjects for more than five half-lives (six months) following study drug administration. The length of the follow-up period may be modified based on drug concentration data observed in this study, as well as ongoing nonclinical data as they become available.

Collection of Serology for SARS-CoV-2 Serostatus. Subjects will be assessed for antibodies against SARS-CoV-2, which may include but not be limited to antibodies against spike (S) and/or nucleocapsid (N) protein, at the screening/baseline visit and (depending on the subject's weight at the time of study drug administration) during scheduled and/or unscheduled visits following study drug administration. These assessments will allow detection of prior SARS-CoV-2 infection and/or seroconversion subsequent to a SARS-CoV-2 infection that occurs during the study.

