The combination of casirivimab+imdevimab therapy should be used during pregnancy or breastfeeding only if the potential benefit justifies the potential risk for the mother and the fetus or breastfed child considering all associated health factors. Pregnancy that occurs during this study will be reported and followed, including any complications and pregnancy outcome, as described in Section 10.1.3.

Other Theoretical Risks. Theoretical risks of casirivimab+imdevimab include interference with the patient's endogenous immune response to either SARS-CoV-2 infection or vaccination against COVID-19. In this study, risk mitigation includes prohibition of SARS-CoV-2 vaccination for 90 days after study drug administration (Section 8.7.1), consistent with current CDC guidance (CDC, 2021b).

Antibody-dependent enhancement (ADE) has been observed for some therapeutics targeting exogenous viral proteins. For antibody therapies, ADE is thought to occur when binding of antibody to the target viral protein enhances Fc gamma receptor (FcγR)-mediated host cell entry of the virus (Iwasaki, 2020). This could potentially lead to worsening of disease and, in the case of SARS, acute lung injury (Liu, 2019). Casirivimab and imdevimab each retain the Fc region, as this may play a role in protecting against viral infection (Yasui, 2014), there is no strong evidence of ADE in other coronavirus models (Kam, 2007) (Liu, 2019) (Luo, 2018). To date, Fc-containing mAbs developed by the Sponsor for Ebola virus and MERS-CoV have demonstrated specificity to their exogenous targets with no significant unexpected safety findings in preclinical or clinical studies. All subjects will have follow-up assessments during the drug elimination period (for over five half-lives; Section 3.2.1), and subjects will be monitored for any signal of ADE.

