5.3. Prior/concomitant Illnesses and Medications

Medications and procedures will be summarized based on SAF using descriptive statistics.

Prior/concomitant medications will be summarized by ATC level 2 and ATC level 4.

Prior/concomitant procedures will be summarized by SOC and PT.

Listings will also be provided.

Participants who received COVID 19 vaccine and their time to first COVID 19 vaccine (days) from the study treatment administration including the following categories: ≤ 90 days and > 90 days, will be summarized using descriptive statistics.

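### Protocol Section 8.7.1 lets a child who has already had the single dose be taken out of the study for using a prohibited medication, which can only shorten observation

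*Protocol*

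**What the plan says.** Protocol Section 8.7.1 bars certain products when used as prophylaxis in SARS-CoV-2-negative children: other investigational drugs, investigational SARS-CoV-2 vaccines, authorized or approved vaccines (within 90 days of dosing or the CDC time frame), and passive antibodies (within 90 days). It then adds: "Use of a prohibited medication during the on-treatment period may result in permanent discontinuation of a subject from the study".

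The other provisions that bear on this are:

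- **Treatment.** Section 8.2.2: "This is a single dose study; study drug discontinuation is not applicable".
- **Follow-up.** Section 3.2.1: "Subjects will undergo a follow-up period of approximately 24 weeks (six months) for assessment of drug concentrations, safety, and immunogenicity". Section 3.3.2: "All subjects will have follow-up assessments during the drug elimination period (for over five half-lives; Section 3.2.1".
- **Endpoint.** Section 4.2 takes TEAEs to end of study, and Section 11.4.3.1 closes the on-treatment period at the last study visit.
- **Withdrawal.** Section 7.3: "An excessive rate of withdrawals would render the study uninterpretable; therefore, unnecessary withdrawal of subjects should be avoided". Section 7.4: "Subjects prematurely discontinued from study will not be replaced".
- **After withdrawal.** The child is asked to attend one early termination visit (Sections 7.3 and 9.1.2). SAEs and AESIs are followed until resolved or stable, and later SAEs judged related remain reportable (Section 10.1.1).
- **Analysis.** SAP 5.4 reports prohibited medication among protocol deviations. Protocol 11.4.4.1 and SAP 5.9.1 allow the PK analysis to be stratified when a child receives a treatment that may alter PK.

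**The concern.** In a multiple-dose trial, a rule that ends participation after a prohibited medication may at least stop further exposure. Here there is nothing left to stop. Once the dose is in, the child carries the drug through the elimination period whether or not anyone is watching, and the sentence in Section 8.7.1 can act only on observation.

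The loss would also depend on something that happens after dosing, namely receipt of a vaccine, a passive antibody or another investigational product. Safety data cut off by a post-dose event are harder to interpret than data lost by chance. Under SAP 5 and 5.8.1, TEAEs are counts and percentages of all children in the group. A child who leaves early therefore stays in the denominator, while later non-serious events go unseen. In a study of about 28 children without replacement, there is little room for avoidable loss.

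**Working it through.** **Inputs.** Section 3.2.1 gives an "observed half-life of approximately 32.4 days (casirivimab) and 27.0 days (imdevimab", taken from COV-2069 and not from children under 12. The last visit is day 169, which is 168 days after dosing, with a window of ±3 days (Table 3). Times below are days after dosing.

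**Step 1: reproduce the plan's figure.** Follow-up in half-lives is days divided by half-life.

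- Casirivimab: 168/32.4 = 5.19. Five half-lives is 5 × 32.4 = 162 days.
- Imdevimab: 168/27.0 = 6.22. Five half-lives is 5 × 27.0 = 135 days.
- At the early edge of the window (165 days): 165/32.4 = 5.09 and 165/27.0 = 6.11.

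The plan's figure of more than five half-lives is reproduced for a child who completes.

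**Step 2: a child discontinued under Section 8.7.1.** The removal time is an assumption, so a range is shown.

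| Removed at (days) | Casirivimab half-lives | Imdevimab half-lives | Days lost of 168 |
|---|---|---|---|
| 28 | 28/32.4 = 0.86 | 28/27.0 = 1.04 | 140 |
| 60 | 60/32.4 = 1.85 | 60/27.0 = 2.22 | 108 |
| 90 | 90/32.4 = 2.78 | 90/27.0 = 3.33 | 78 |

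At 90 days the child is 162 − 90 = 72 days short of five half-lives for casirivimab and 135 − 90 = 45 days short for imdevimab, and has lost 78/168 = 46% of the planned days. If decline is first-order at these half-lives, about 15% and 10% of drug remains at that point. Removal by 90 days therefore cannot meet the five-half-life statement for either antibody. Investigational drugs and investigational vaccines carry no time limit, so removal could also come later. Anything before 135 days falls short for both antibodies, and anything before 162 days falls short for casirivimab.

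**Step 3: what is lost, by type of data.**

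- *Adverse events.* All scheduled AE contacts after the early termination visit. This is the main loss.
- *PK-ADA samples.* As far as Table 3 can be read, the last scheduled sample is day 57 on schedule 1 and day 113 on schedule 2. A schedule 1 child who leaves 60 days after dosing loses none. A schedule 2 child loses days 85 and 113, partly offset by the early termination sample.
- *ADA.* Footnote 15 to Table 3 names day 29 (schedule 1) and day 85 (schedule 2) as the post-dose ADA time points. A child who leaves before that day has a post-dose ADA result only if another sample, such as the early termination sample, is tested. Without one, the child is outside the ADA analysis set (Protocol 11.3.3, SAP 3.3).
- *Grade 3 or higher injection site and hypersensitivity reactions.* This endpoint closes at day 4 and is barely touched.

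**Step 4: number of children.** The documents give no expected frequency. At planned numbers one child is 1/12 = 8.3% of a minimum-size weight group and 1/28 = 3.6% of the study. That is the weight of one child, not an estimate of effect.

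**The case against.** The strongest reply is that the sentence says *may*. Section 7.3 already tells sites to avoid unnecessary withdrawal, and read together the two sections can be taken to limit the discretion. Exclusion criteria 7 and 8 remove children who are part-way through vaccination or plan a vaccine within 90 days. Children given an authorized or approved vaccine after the restricted period stay in. A child who is discontinued still has an early termination visit and SAE/AESI follow-up. All of this stands. It means that follow-up is shortened rather than wholly lost, and perhaps rarely. It does not give the sentence a purpose in a single-dose study, and PK confounding can already be handled by stratification.

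Two stronger readings are tempting, and the documents support neither:

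- *That the rule removes the very children whom the follow-up was designed to study for vaccine interference.* Section 3.3.2 names that theoretical risk, but its stated mitigation is the 90-day prohibition. The five-half-life sentence belongs to the discussion of antibody-dependent enhancement, and no endpoint or study variable measures vaccine response. Amendment 2 also calls enhancement no longer relevant while Omicron dominates. The follow-up argument does not depend on enhancement, however, because Section 3.2.1 separately ties the same period to drug concentration and safety.
- *That the SAP assumes these children stay in.* SAP 5.3 summarizes "Participants who received COVID 19 vaccine and their time to first COVID 19 vaccine (days) from the study treatment administration", split at 90 days. That needs only two dates, both of which can be known for a child who then leaves. Reporting a deviation under SAP 5.4 is compatible with staying or leaving.

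**Conclusion.** The point holds as a should-fix matter of internal consistency and data retention. Section 8.7.1 permits, without requiring, an action that has no treatment to stop and that cuts short the follow-up promised for all children and the end-of-study TEAE endpoint. For removal by 90 days after dosing, follow-up is at most 2.8 and 3.3 half-lives instead of 5.2 and 6.2, with at least 78 of 168 days lost. These figures rest on the protocol's COV-2069 half-lives and an illustrative removal time. The effect on the study's results cannot be computed, because neither the frequency of prohibited use nor how often the discretion would be exercised is given. SAP 1 also reports that enrollment was paused on December 28, 2021, so the planned 28 may not be the number dosed.

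**What to change.** Replace the final sentence of Section 8.7.1 with wording to this effect: use of a prohibited medication is recorded as a protocol deviation, as in SAP 5.4, and is not by itself a reason to discontinue the subject from the study; the subject continues the remaining scheduled safety visits through day 169 and any PK-ADA samples still due on the assigned schedule, unless consent is withdrawn or withdrawal is in the subject's interest under Section 7.3.

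The exception for the child's interest must stay, so that the new sentence does not override Section 7.3. The wording should promise only the PK-ADA samples on the assigned schedule, since sampling appears to end before day 169.

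In the data, flag PK and ADA samples taken after a product that could interfere, and use the flag in listings and in the stratification that Protocol 11.4.4.1 and SAP 5.9.1 already allow.

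The prohibited list, the dose and clinical care are untouched. The cost is one protocol sentence and one flag. The small downside is that some later samples will come from children exposed to a confounding product, which the flag makes visible.
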